Subjects who are indicated for cervical spine surgery will be screened for inclusion in the study. If the subject meets all of the eligibility criteria and agrees to participate in the study after informed consent, they will be enrolled to complete multiple phases of testing with the driving simulator set-up. Subjects will be divided into the following groups: single-level anterior cervical discectomy fusion (s-ACDF), multi-level anterior cervical discectomy and fusion (m-ACDF), cervical disc replacement (CDR), posterior laminectomy and fusion (PCLF), posterior cervical decompression procedure (PCD). Each group will contain a total of 30 subjects. The study will evaluate and compare peri-operative changes in driving performance following these procedures. We will evaluate driving performance at the pre-operative time period as well as 2-weeks, 6-weeks and 3-months post-operatively. A group of 40 healthy volunteers will also be tested with the driving simulator to serve as controls.

The primary hypothesis of this study is that there is a temporal effect on patient's driving ability after cervical spine surgery. We believe that pre-operative and post-operative clinical and functional measures will have an impact on driving performance. Pre-operative measures include pre-operative driving performance measures, neck disability index (NDI), PROMIS, numeric pain rating scale (NRS), pre-operative diagnosis, comorbidities, clinical and physical exam measures, maximum axial rotation of neck and torso, narcotic usage, questionnaire responses and demographic information. Post-operative measures include post-operative driving performance, type of surgery, complications, radiological outcomes, neck disability index (NDI), PROMIS, numeric pain rating scale (NRS), clinical and physical exam measures, maximum axial rotation of neck and torso, narcotic usage and questionnaire responses.

II. BACKGROUND

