- Measurement of cervical and thoracic axial range of motion using video motion capture technology
- Field of view testing
- 10s grip and release test, 10s step test, Tandem Gait (heel-to-toe) walk*
- Testing of driving performance using a customized driving simulator set-up
- All other procedures are standard of care for all investigators involved

- E. ***These tests tend to be done as part of standard of care identifying myelopathy patients, but in the case it is not performed as standard of care we will perform the tests as a research procedure. Only clinical research staff or non-clinical staff trained to perform the tests will perform the tests. For non-clinical staff who received training, we will still ensure a clinician is in close proximity if help is needed while doing the tests.**

INCLUSION CRITERIA

- *Study Subjects:*
 - Age between 18 and 80 years
 - Indicated for elective cervical spine surgery (including ACDF [single or multi-level], posterior cervical laminectomy and fusion, posterior cervical laminoplasty, posterior cervical foraminotomy, cervical disc replacement) after failing at least 6 weeks of non-operative treatment modalities
 - Valid driving license
 - Regular use of a vehicle
 - Signed consent form
- *Control Subjects:*
 - Age between 18 and 80 years
 - No pre-existing or recent injuries to neck, torso, back
 - No neurologic or systemic debilitating conditions
 - Valid driving license
 - Regular use of a vehicle
 - Signed consent form

F. EXCLUSION CRITERIA

- Significant visual impairment
- Significant debilitating neurological condition with loss of function of one or more extremities
- Recent extremity surgery
- Recent eye surgery
- Previous history of motion sickness, vertigo in simulated settings
- Recent history of chemical or narcotic dependency

G. VULNERABLE POPULATION

Students and faculty of NYU School of Medicine and NYU Langone Medical Center will be recruited as potential control subjects and will be eligible to participate in the study. Students and faculty can voluntarily participate in this study without coercion. The Principal Investigator, Sub-Investigators, and research staff will ensure there are additional safeguards for these subjects. They will

NCT02782923

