emphasize that neither the subjects' academic status, grades, and/or employment will be affected by their decision to participate or not. The principal investigator, sub-investigators, and research staff will ensure that the subjects' record of participation cannot be linked to any type of academic or employee record. The Principal Investigator will ensure that the research design addresses such institutional pressures and preserves the right for subject to refuse participation

Subjects 65 years of age or older will also be recruited as potential subjects and will be eligible to participate in the study if their treating surgeon deems them eligible.

H. POTENTIAL BENEFITS

There are no absolute benefits for the patient or volunteer to complete this study. Patients may potentially become more aware of their post surgical condition and it may affect their ability to drive. Furthermore, from subject participation in the study, there will be a better understanding of the impact cervical spine surgery has on driving performance. This can then allow practitioners to make evidence-based recommendations regarding changes in driving performance in the post-operative period.

I. ADVERSE EVENTS/RISKS

There are no significant risks associated with this study. The driving simulator set-up has been used in three previous studies by the investigators and no adverse events have been reported. The simulated driving scenario can potentially result in motion sickness during the trial. Additionally, there is the possibility that axial rotation of the neck and/or torso may cause the patient discomfort when driving.

J. PROTECTION AGAINST RISKS

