The study subjects will be instructed to inform the research coordinator if they experience motion sickness or discomfort. The simulated trials will be stopped immediately and the study subject will be asked if they would like to complete the trial. If the study subject does not wish to complete the trial, they will have the option to complete the trial at a later date or be removed from the study. The investigators are familiar with the protocol and have utilized this driving simulator in previous studies. For data collection, the research coordinator is knowledgeable in the field of orthopaedic care and clinical research. All personnel have completed CITI training and the investigators have a dedicated staff and nurse to attend to the patient's medical and psychological needs if needed. If patients require medical monitoring, ancillary care, or equipment, patients will be able to seek care in case of an emergency at the NYU-HJD Immediate Care Center, which is open 24/7. The research coordinator, will also be available to patients during regular office hours.

K. INVESTIGATION SCHEDULE AND FOLLOW-UP

Data will be collected regarding individual patient demographics, pre-operative diagnosis, procedure and driving history at the pre-operative and first post-operative time period. Patient-reported outcome instruments (NDI, PROMIS, NRS), physical exam measures, narcotic usage, driving performance measures, a post-simulated driving questionnaire and maximal axial rotation of the neck and torso will be collected at all time points. The EQ5D and mJOA survey will be collected only

NCT02782923

from myelopathy patients at baseline, 3 month, and 6 month. This data will be recorded onto a de-identified data collection sheet by the researchers. The patient data sheets will then be entered into a protected electronic database, while the data sheets will be stored as a back-up until the study is complete. Once the completed database is analyzed and summarized, the results will be presented to the involved participants without any identifiable patient information. Follow-up will be the investigators' routine follow-up at 2 weeks, 6 weeks, 3-months, and 6 month post-operatively. The 6 month routine follow up is unique to myelopathy patients only.

L. CASE REPORT FORMS**1. PRE-OPERATIVE VISIT**

- a. Informed consent
 - i. If informed consent is not obtained at pre-operative visit, the visit will not continue.
- b. Investigator Form (Complete Sections 1-9)

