- a. Case report forms and all other documentation collected by the investigators and research coordinator/assistant will not contain subject names. Each subject will be assigned a subject code. The subject code will consist of 8 characters in an alphanumeric combination. The site will maintain the link between the subject code and the names. Primary data collection will be based on source-documented hospital chart reviews, notes on the source worksheets and subject interviews will be performed by study coordinators/researchers or investigators at each clinical site. Data will be stored in individual subject binders and locked in a secure office. Only approved research coordinators/investigators will have access to the data.
5. Assessments

NCT02782923

- a. Safety reviews will be performed monthly by the monitoring entity (the principal investigator). The monitoring entity will be responsible for determining the relationship of an adverse event and the treatment received. Since the PI sees the subjects regularly for follow up visits, he will be familiar with the subjects' outcomes and patient histories, thereby making it easier to detect AEs if they do arise. This plan allows for prompt detection of unanticipated problems involving risks to subjects.
 - b. Monitor the incidents of pseudoarthrosis for both graft groups
6. Criteria for Action
- a. Subject stopping will occur if any adverse events occur that are level 4 or above, or if the subject is unlikely to comply with the follow-up evaluation schedule
 - b. Study stopping will occur if there patients experience persistent pain following the simulator trials
 - c. Study stopping will occur if patient cannot tolerate the simulator due to motion sickness
7. Data Storage and Confidentiality
- a. Case report forms and all other documentation collected by the investigators and research coordinator will not contain subject names. Each subject will be assigned a subject code. The subject code will consist of 8 characters in an alphanumeric combination. The site will maintain the link between the subject code and the names. Primary data collection will be based on source-documented hospital chart reviews, notes on the source worksheets and subject interviews will be performed by study researchers or investigators at each clinical site. Data will be stored in individual subject binders and locked in a secure office. Only approved research coordinators/investigators will have access to the data.

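### Criterion 6(c) makes one patient's simulator intolerance a reason to stop the whole study, while the rest of the protocol handles it subject by subject

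*Protocol*

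**What the plan says.** Section letters here follow the body of the protocol. From G onward the table of contents runs one letter behind.

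- **Criteria for Action (IV.O, item 6)** has two levels of action. Item (a) is subject-level: "Subject stopping will occur if any adverse events occur that are level 4 or above", or if follow-up compliance is unlikely. Items (b) and (c) are study-level. Item (b) concerns persistent pain after the simulator runs and speaks of patients in the plural. Item (c) reads "Study stopping will occur if patient cannot tolerate the simulator due to motion sickness", in the singular.
- **Protection Against Risks (IV.J)** covers motion sickness and discomfort: "The simulated trials will be stopped immediately and the study subject will be asked if they would like to complete the trial". For a subject who does not wish to go on, "they will have the option to complete the trial at a later date or be removed from the study". In this section, trial means the simulator run, not the study.
- **Study Design, Driving Simulator (IV.N)** halts the scenario when a subject reports feeling uncomfortable.
- **Subject Withdrawal Criteria (IV.C)** provides for recruiting new subjects in place of those who withdraw.
- **Adverse Events/Risks (IV.I)** acknowledges the event: "The simulated driving scenario can potentially result in motion sickness during the trial". It also reports past experience: "The driving simulator set-up has been used in three previous studies by the investigators and no adverse events have been reported".
- **Exclusion Criteria (IV.F)** lists "Previous history of motion sickness, vertigo in simulated settings".

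**The concern.** A stopping criterion is a decision rule that the investigators commit to in advance. Criterion 6(c) gives a study-level action to an event in one person and has no threshold. The protocol foresees that event, and the exclusion criterion screens only people with a known history, so a first episode during the study remains possible.

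If a patient definitively cannot tolerate the simulator, 6(c) applied as written would stop a study of 210 planned subjects because of that patient. Carrying on instead would depart from a written stopping criterion. The protocol does not define stopping, so whether 6(c) means a pause or a permanent end is also open. At stake is whether the study can finish under its own rules. No estimate, endpoint or error rate is at issue.

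**Working it through.** The protocol attaches no figure to this criterion, so there is none to reproduce. The check sets the provisions side by side and follows one patient through them.

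| Situation | IV.J, IV.N and IV.C | Criterion 6(c) as worded |
|---|---|---|
| Feels sick, recovers, completes the run | Run is stopped, then completed | Not triggered: the patient can tolerate the simulator |
| Feels sick, returns on a later date and completes | Run is postponed | Not triggered |
| Definitively cannot tolerate the simulator | Subject is removed; subjects who withdraw are replaced | Triggered: study stopping |

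**Step 1: where they diverge.** The first two rows are compatible. Only the third gives different results.

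**Step 2: what the third row shows.** IV.J states what happens to the subject and does not say whether the study continues. Continuation is inferred. Offering to remove one subject makes little sense if the same event ends the study for everyone. IV.N halts only the scenario, and IV.C foresees recruiting substitutes. Replacement comes from IV.C, not from IV.J.

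**Step 3: is the level of action in 6(c) deliberate?** Item 6(a) shows that the authors had a subject-level category available. Item 6(b), also study-level, uses the plural, while 6(c) uses the singular and states no number. This points to a slip for subject-level stopping. It is not proof, because the wording around it is loose: 6(b) is itself ungrammatical.

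**Step 4: size.** The chance of at least one trigger among n patients would be 1 − (1 − p)^n, with p the per-patient probability of definitive intolerance and patients taken as independent. The protocol gives no p, so the formula cannot be evaluated from the document. What can be counted is exposure:

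- Operated patients: "Each group will contain a total of 30 subjects" and there are five surgical groups, so 5 × 30 = 150.
- Required drives per operated patient: 1 pre-operative + 3 post-operative (2, 6 and 12 weeks) = 4.
- Scheduled drives: 150 × 4 = 600.
- All planned subjects: 150 + 20 non-operated myelopathy patients + 40 controls = 210, matching the total in IV.C.

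The 600 counts occasions on which the rule could apply to operated patients. Without a rate it measures neither likelihood nor harm.

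**Step 5: who is covered.** Criterion 6(c) says patient, which might seem to leave out the controls. The protocol uses that word loosely: IV.C describes all 210 subjects, controls included, as groups of patients. A repaired rule should therefore refer to subjects.

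**The case against.** The strongest reply is that the protocol already shows what to do. IV.J gives a usable instruction, IV.N stops only the scenario, IV.C provides substitutes, and IV.O item 2 leaves stopping or modifying the protocol to the investigators. On this view 6(c) is an editorial blemish that nobody would apply literally. Much of that stands, and it is why the point is minor. It does not make the sentence right: a listed stopping criterion gives an unreasonable result if followed.

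One could also read study stopping in 6(c) as ending that patient's participation. That is probably the intent, but 6(a) already has a separate term for it, so the wording needs correction on this reading too.

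Two stronger readings are tempting, and the document supports neither.

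- A reader might infer that IV.J and 6(c) are flatly contradictory, so that staff cannot obey both. IV.J is silent on the fate of the study. Removing the subject and stopping the study could both be done. The tension comes from what IV.J, IV.N and IV.C jointly imply.
- A reader might infer that 6(c) would probably end the study. That needs an intolerance rate, and any probability quoted would only reflect the rate assumed. What evidence the protocol offers points to a low rate: no adverse events reported in three earlier studies with this set-up, and exclusion of people with the relevant history.

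**Conclusion.** The point holds in limited form. Criterion 6(c) is wrong as written: it sets a one-patient, study-level trigger for a foreseeable event that other sections manage individually. Read literally, the first definitively intolerant patient would stop the study.

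This rests on two inferences. The first, that the study is meant to continue after a subject is removed, is well supported by three sections together. The second, that subject-level stopping was meant, is likely but not certain.

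Severity is minor. No trigger probability can be given, the practical guidance in IV.J is workable, and sample size and analysis change only if the study is actually stopped.

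**What to change.** Replace 6(c) with wording such as: *Subject stopping applies when a subject, after the steps under Protection Against Risks (Section J), definitively cannot tolerate the simulator because of motion sickness; that subject is removed and replaced as under Subject Withdrawal Criteria.*

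This wording covers controls as well as patients. It leaves completing or postponing a run outside the definition of stopping, and it names the section that provides for replacement. If a study-level rule was intended, keep it as a separate item with a stated number or proportion of intolerant subjects, and say whether stopping means a pause for review or termination.

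The cost is one sentence in a protocol amendment, with no effect on data or sample size.
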